14.8.2. Pairing Scheme

All YSI^{™*} and fingerstick values collected will be presented. Descriptive analyses will include all YSI^{™*} values, such as those less than (<) 40 mg/dL, or greater than (>) 400 mg/dL as long as Guardian[™] Sensor (3) values are greater than or equal to (≥) 40 mg/dL or less than or equal to (≤) 400 mg/dL. Reference glucose values (YSI^{™*} values) will be paired with the closest Guardian[™] Sensor (3) value between [0, 5) minutes. Reference glucose values (fingerstick values) will be paired with the closest Guardian[™] Sensor (3) value between (-5, 0] minutes. The primary Guardian[™] Sensor (3) will be used as a reference for precision analysis and the pairing scheme will be [0, 5) minutes.

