5.1 Study Design

This study is a multi-center, prospective single-arm design without controls. Up to 72 subjects will be enrolled in order to have approximately 60 subjects complete the study. Three investigational centers in China will be used during this study.

During the study, each subject will be randomly assigned to one day of the Yellow Springs Instrument (YSI^{TM*}) frequent sample testing (FST) (Day 1, 3-5, or 7). Subjects will wear two GuardianTM Sensor (3)s each connected to a GuardianTM Connect transmitter for approximately 7 days (one which will be paired to the Guardian Connect app and the other will function as a glucose recorder.).

The Guardian Sensor (3)s will be worn in the abdomen area and self-inserted by the subject on same side or opposite sides.

On the evening prior to FST, subjects will be asked to fast for approximately 12 hours and adjust their insulin and medications according to routine care (for example as they would do for fasting lipid panel). Subjects may fast for shorter period of time based on investigator discretion.

The subject should be in fasting status upon arrival at hospital to start FST process. The feeding protocol may be modified based on investigator discretion.

The duration of FST will be approximately 7 hours.

During the study, subjects will continue with their current diabetes regimen independent of the study devices. Subjects will be instructed by the investigational center that they are not to use the study devices (except for the CONTOUR^{TM*} study meter) for the management of their diabetes. The CONTOUR^{TM*} study meter may be used for treatment decisions and calibration of GuardianTM Sensor (3).

Calibration at Home: Calibration at home will be required to be 3-4 times spread throughout the day for the GuardianTM Connect app.

Calibration should also be performed if the Guardian™ Connect app prompts for calibration (i.e., Smart calibration feature). NOTE: Subject will be instructed to minimize the delay time between prompt and calibration.

Fingerstick Testing: Fingerstick testing will be recommended to be a minimum of 4 times spread throughout the day. Subjects should test prior to and following meals and at bedtime.

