6.6 General Considerations for Data Analysis

6.6.1 Data Collection

Analysis data source: The analysis of primary endpoints, other descriptive endpoints and simulation alert calculation will be based on both Oracle Remote Data Capture (RDC) database and external device dataset (collected sensor glucose data). The detailed specification of variables from external device data are as following:

- SG: Raw Sensor Glucose Reading
- PSGV: Predicted Sensor Glucose Reading
- SBG: Sensor Blood Glucose (values below 40 display as 40, values above 400 display as 400) elaborated below
- ROC: Rate of Change of SG
- ISIG: Interstitial Signal
- FORCALBG: Used in Calibration

The value "511" in the SG and PSGV column indicates "null". The SBG column will display saturated values of 40 if the reading was displayed as "Low" (i.e. if SG < 40 mg/dL) or 400 if the reading was "High" (i.e. if SG > 400 mg/dL) while the SG column will display 511. SG value of 40 is indicated when SG and SBG columns are equal to 40, and same for 400. SG column is used to generate the numerical calculation for sensor performance. SBG is used for alert analysis and sensor life analysis. PSGV and ROC columns are used for alert analysis.

In addition, primary endpoints, other descriptive endpoints, and functional sensor life time will be based on real-time data collected from primary sensor. Precision analysis will be based on data collected from both sensors.

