7.12 Simulation Alert Calculation

The simulation alert calculation for the device 640G Pump and GS3 (Guardian™ Sensor 3) APP will be provided based on data collected in OC-RDC database and external device database.

- (1) Dataset preparation: The device dataset is prepared for alert calculation. The valid data should be after first valid ISIG. Any data before first valid ISIG should be excluded from analysis.
 - (2) Variables used for calculation: SBG, PSGV, ROC, and YSI^{TM*}/MBG where applicable.
- 1) SBG (Saturated Sensor Blood Glucose) is used for threshold alert analysis. Note: SBG is a saturated SG when SG <40, it sets to 40 or 400 when SG>400.
- 2) PSGV (Predictive Sensor Glucose Reading) is used for hypo predictive alert analysis of 640G Pump
- 3) ROC (Rate of Change of SG) is used for hyper predictive alert analysis of 640G Pump and for both hypo and hyper predictive alert analyses of GS3 APP. ROC-based predictive SG will be calculated with the formula: PSGV=SBG+ROC*30.
- (3) The CGM Setting: For hypo range, the CGM alert settings will be set as <= 50/60/70/80/90/100 mg/dL, respectively. For hyper range, the CGM alert settings will be set as >=300/250/220/180 mg/dL, respectively. Reference value YSI^{TM*} and SBG/PSGV threshold will keep changing as alert setting changes.
- (4) Calculation indicators and methods: Detection rate, missed detection rate, false alert rate and true alert rate will be calculated. For these four indicators, three types of simulation alert/event rates will be calculated. These three types are threshold, predictive and combined threshold and predictive, respectively. The detailed definition of above four indicators are below:
- 1) Detection Rate (% of Hypo/Hyper Events Correctly Detected): The device alarmed at the specified CGM settings within 30 minutes (or 15 minutes) before or after the reference blood glucose

value (YSI™* or MBG) goes at/below (for hypo) or at/above (for hyper) the specified CGM setting levels.

- 2) Missed Detection Rate (% of Hypo/Hyper Events Not Detected): The device did not alarm at the specified CGM settings within 30 minutes (or 15 minutes) before or after the reference blood glucose value (YSI^{TM*} or MBG) goes at/below (for hypo) or at/above (for hyper) the specified CGM setting levels.

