- 3) False Alert (% False Alerts): There is no reference blood glucose value (YSI or MBG) goes below (for hypo) or above (for hyper) the specified CGM setting levels within 30 minutes (or 15 minutes) before or after the sensor alarmed at the specified alert settings.
- 4) True Alert (% of Alerts Verified by Hypo/Hyper Events): There is at least one reference blood glucose value (YSI or MBG) goes below (for hypo) or above (for hyper) the specified CGM setting levels within 30 minutes (or 15 minutes) before or after the sensor alarmed at the specified alert settings.

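### In the SAP 7.12 alert analysis, a calibrating meter reading can verify an alarm computed from it, so meter-referenced detection and true-alert rates are expected to be too favourable

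*SAP*

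**What the plan says.** SAP 7.12 gives the inputs as "Variables used for calculation: SBG, PSGV, ROC, and YSI^{TM*}/MBG where applicable". I read MBG as meter blood glucose. Detection is credited when "The device alarmed at the specified CGM settings within 30 minutes (or 15 minutes) before or after the reference blood glucose" value reaches the alert setting, and a missed detection is the converse in the same window. True and false alerts use the window turned round: an alarm is true if a qualifying YSI or MBG value lies "within 30 minutes (or 15 minutes) before or after the sensor alarmed at the specified alert settings", and false if none does. Section 7.12 does not separate calibrating readings from other meter readings, although SAP 6.6.1 lists among the device variables "FORCALBG: Used in Calibration".

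SAP 5.1 says "Calibration at home will be required to be 3-4 times spread throughout the day", with further calibrations whenever the app prompts. For meter testing it says "Fingerstick testing will be recommended to be a minimum of 4 times spread throughout the day", and the next sentence asks for tests before and after meals and at bedtime. Protocol 9.2.4.3 tells subjects to calibrate only with the study meter. Protocol 7.1.4 says that the transmitter's algorithm turns the sensor signal into a glucose value using entered meter values. SAP 6.6.4 also retains sensor data reprocessed with additional meter readings.

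Protocol 14.8.2 has a one-sided rule for point pairing: "Reference glucose values (fingerstick values) will be paired with the closest" sensor value in (-5, 0] minutes, that is, at or before the stick. SAP 6.6.2 has no fingerstick pairing rule, and SAP 7.13 does not list that as a change.

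**The concern.** A reference should be independent of the device under test. Once a low or high meter reading has been entered as a calibration, the sensor values behind the simulated alarms (SBG, PSGV, ROC) depend on it. An alarm a few minutes later can then be scored as a detection of that reading and as a true alert verified by it. A meter error would be passed to the sensor and then confirmed by the same meter value. Even where calibration makes the sensor more accurate, such an alarm does not show that the device would have found the event without the fingerstick.

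Alert performance is a listed descriptive endpoint (Protocol 5.2.2). Alerts are switched off during the study (Protocol 7.1.1), so the endpoint rests wholly on this retrospective calculation. YSI values exist only for one session of about 7 hours per subject. Outside that session, meter readings are the only reference.

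**Working it through.** The plan states no target or expected rate for the alert analysis, so there is no figure to reproduce.

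**1. Share of meter readings that calibrate** = calibrations per day / meter readings per day. Inputs from SAP 5.1: 3-4 calibrations; at least 4 readings. Three meals a day (my assumption) give 3 before + 3 after + 1 bedtime = 7 readings.

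| Readings per day | 3 calibrations | 4 calibrations |
|---|---|---|
| 4 | 3/4 = 75% | 4/4 = 100% |
| 5 | 60% | 80% |
| 6 | 50% | 67% |
| 7 | 3/7 = 43% | 4/7 = 57% |
| 8 | 38% | 50% |

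One Smart calibration on top of four gives 5/7 = 71% at 7 readings a day. The documents do not say how many such prompts to expect.

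**2. Share of all references if YSI and MBG were pooled.** Assume 15-minute draws throughout a 7-hour session, 7 × 60/15 + 1 = 29 YSI values, and 7 days of meter readings. The calibrating share runs from 21/(49 + 29) = 27% (7 readings, 3 calibrations a day) to 28/(28 + 29) = 49% (4 and 4).

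**3. Which part of the window is affected.** Take a calibrating MBG of 60 mg/dL at an alert setting of 70 mg/dL.
- An alarm at or before the reading was computed without it. It is a valid detection and a validly verified alert.
- An alarm after the reading, with none before, was computed partly from it. SAP 7.12 scores it as a detection and as a true alert. This is the circular part.

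**4. Illustrative size.** A simulation of threshold alarms at 80 mg/dL or below, using the 30-minute window, 7 readings and 4 calibrations a day. Assumed, with no source in the documents: sensor bias SD 18%, meter error SD 6%, and a calibration that removes 0%, 50% or 80% of the bias.

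| Bias removed | Reading | Events | Detected, two-sided | Detected at or before | Added by after-half |
|---|---|---|---|---|---|
| 0% | calibrating | 345 | 84.1% | 80.0% | 4.1% |
| 0% | other | 254 | 82.7% | 76.0% | 6.7% |
| 50% | calibrating | 353 | 91.5% | 80.2% | 11.3% |
| 50% | other | 261 | 89.7% | 85.1% | 4.6% |
| 80% | calibrating | 329 | 96.0% | 82.7% | 13.4% |
| 80% | other | 230 | 86.1% | 78.7% | 7.4% |

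The last column separates window width from circularity. Readings that do not calibrate also gain 5-7 points from the after-half, because the window is wider. The excess at calibrating readings is 4.1 - 6.7 = -2.6 points with no calibration effect, 11.3 - 4.6 = +6.7 at 50%, and 13.4 - 7.4 = +6.0 at 80%. The standard error of the 80% contrast is √(0.134 × 0.866/329 + 0.074 × 0.926/230) = 2.6 points, ignoring within-subject correlation. The direction is as expected. The size is not a property of this device.

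**5. Effect of deleting all flagged readings.** If an alarm precedes a low calibrating MBG and that MBG is deleted, SAP 7.12 finds no qualifying reference in the window and scores the alarm as false, although it was a genuine prior detection. With 43-100% of meter readings removed, this would bias the false-alert rate against the device.

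**The case against.** The strongest reply is that this is a descriptive analysis with no hypothesis or threshold, that YSI-referenced rates are untouched, and that the extent of meter use is left open. Section 7.12 never says 'home', leaves 'where applicable' undefined, and in item (3) names only YSI as the reference that moves with the alert setting. The mock tables cited in SAP section 9 are not in the text reviewed and may already show the two references separately. All of this stands, and it limits the weight of the point. It does not remove it: the four definitions name MBG as a reference, and nothing in the text excludes a calibrating reading.

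Four stronger readings are tempting, and the documents do not support them.
- That most meter readings are calibrators. This holds at the 4-fingerstick minimum but is not assured under the meal-and-bedtime schedule.
- That the bias always favours the device. Only the after-reading half of the window is circular for that reading, and the documents do not describe how strongly or quickly a calibration moves SBG, PSGV or ROC. The mechanism mainly adds self-verified alarms; it does not in general turn existing false alerts into true ones.
- That Protocol 14.8.2 sets a safeguard against circularity which the SAP dropped. Its rule pairs one fingerstick with one sensor value. It is not an alert-window rule, and no such reason is given for it. It is a useful precedent only.
- That the whole gain from a two-sided window is circular. Part of it is window width, as step 4 shows.

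**Conclusion.** The point holds for MBG-referenced rates. Followed as written, SAP 7.12 lets a calibrating reading verify an alarm computed from it. Detection and true-alert rates against MBG are therefore expected to be too high, and missed-detection rates too low. The calibrating share is large, 75-100% at 4 readings a day and about 43-57% at 7 (three meals assumed), and higher with Smart calibrations. The amount of bias cannot be fixed from the documents. The excess of about 6-7 points in detection at calibrating readings rests on assumed sensor error, meter error and calibration strength. YSI-referenced rates and the four pass/fail criteria are unaffected. This is a worthwhile, low-cost correction to a descriptive endpoint.

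**What to change.** Amend SAP 7.12 as follows.

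1. Report YSI-referenced and MBG-referenced alert rates separately, with the YSI-referenced rates as the main result.
2. For an MBG flagged FORCALBG, or used in reprocessing under SAP 6.6.4, credit detection only for alarms at or before the MBG time.
3. For true and false alerts, do not let such an MBG verify an alarm that follows it. Where that alarm has no other reference in its window, set it aside as not evaluable, do not count it as false, and report the number set aside.

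Do not simply delete all calibrating MBG while keeping every alarm, for the reason in step 5.

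The cost is SAP wording, a filter on a variable already in the device file, a list of any readings used in reprocessing, and a time restriction. No new data are needed. The downside is fewer evaluable MBG events and alarms, and somewhat lower MBG-based rates.

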	"p"; deleted reference stating data from home use study will be described; added Gail-Simon test to address pooled investigative study centers; deleted Difference Tables Comparing Sensor and Reference Reading and Sensor Calibration sections; Updated Other Accuracy Analyses section to delete discussion of Bland-Altman plots and paired differences plots, deleted alert performance characterization, and performance metrics reference; deleted Home-Use Portion Data Analysis section to remove reference to describing home-use data.	
	 Updated version number and version date. 	
	Corrected minor typographical errors.	
	Updated Version History table.

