6.6.4 Sensor Data Retention

All collected sensor glucose data from the study will be analyzed. It includes, but is not limited to, sensor glucose data reprocessed with additional MeterBGs collected by patients.

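### SAP 7.12 counts a simulated alert with no reference value nearby as false, so if alerts outside the FST are scored, the true and false alert rates depend on how often subjects tested

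*SAP*

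**What the plan says.** SAP 7.12, item (4), defines four alert indicators. A false alert is one where "There is no reference blood glucose value (YSI or MBG) goes below (for hypo) or above (for hyper) the specified CGM setting levels" in the 30 (or 15) minutes either side of it. The true alert definition opens "There is at least one reference blood glucose value (YSI or MBG) goes below (for hypo) or above (for hyper" and uses the same settings and window. The only data exclusion is in item (1): "The valid data should be after first valid ISIG. Any data before first valid ISIG should be excluded from analysis".

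The SAP does not say which alerts are scored:

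- **Pointing to all wear.** Meter values (MBG) are named as a reference in all four definitions. SAP 6.6.4 states that "All collected sensor glucose data from the study will be analyzed".
- **Pointing to the FST only.** Item (2) admits YSI or meter values only where they apply. Item (3) names YSI alone as the reference when it says the "threshold will keep changing as alert setting changes". SAP 6.6.2 gives a pairing rule for YSI but none for fingersticks.

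The boundaries also differ. For hypoglycaemia "the CGM alert settings will be set as <= 50/60/70/80/90/100 mg/dL", and a detected event is one where the reference "goes at/below (for hypo) or at/above (for hyper) the specified CGM setting levels". Both include the setting itself. The true and false alert definitions require a value strictly beyond it.

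**The concern.** A false alert should mean that the sensor alarmed and a reference contradicted it. As defined, it also covers an alarm that no reference could confirm or contradict. During the FST this hardly matters, because blood is drawn every few minutes. Outside the FST the reference is a handful of fingersticks a day, so most of the day has no reference nearby.

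Alert performance is a listed descriptive endpoint (Protocol 5.2.2), and 7.12 is the only alert analysis in the body of the SAP; it covers the 640G pump and the app. If alerts over the whole wear are scored, a reader could not tell sensor error from absence of a test, and the rates would move with testing habits while the sensor stayed the same.

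**Working it through.** The plan states no expected alert rate or coverage, so there is no figure of its own to reproduce. The check asks what share of correct alerts the rule would label false.

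**Inputs from the documents**
- Wear: 170 h (SAP 5.4).
- One FST of about 7 h, and a recommended minimum of 4 fingersticks a day (SAP 5.1).
- Home calibration 3–4 times a day (SAP 5.1). The documents do not say whether these tests are additional to the fingersticks.
- Windows: ±30 and ±15 min (SAP 7.12).
- YSI draws at most 23 min apart (Protocol 9.9.1).

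**Assumptions**
- n = 4, 7 or 10 fingersticks a day. Seven is 4 + 3; ten is an assumed upper value.
- Fingerstick windows do not overlap.
- Every alert is correct, and any reference in its window confirms it.
- Alerts are r times as dense in time near a reference as elsewhere. The documents give no value for r, so a range is shown.

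**Step 1: share of wear with a reference in the window.** C = [F + (170 − F) × n × w/24]/170. Here w is the window width in hours, and F is the FST plus half a window at each end.

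- ±30 min (F = 8, w = 1): n = 4 gives (8 + 162 × 4/24)/170 = 35/170 = 0.206; n = 7 gives 0.325; n = 10 gives 0.444.
- ±15 min (F = 7.5, w = 0.5): 0.124, 0.184 and 0.243.

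**Step 2: share of correct alerts scored false.** (1 − C)/[(1 − C) + rC]. For n = 4, r = 5, ±30 min: 0.794/(0.794 + 5 × 0.206) = 0.435.

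| Window | r | n = 4 | n = 7 | n = 10 |
|---|---|---|---|---|
| ±30 min | 1 | 79% | 68% | 56% |
| ±30 min | 2 | 66% | 51% | 39% |
| ±30 min | 5 | 44% | 29% | 20% |
| ±30 min | 10 | 28% | 17% | 11% |
| ±15 min | 1 | 88% | 82% | 76% |
| ±15 min | 5 | 59% | 47% | 38% |

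For the share to fall to 10% at ±30 min, r must equal 9(1 − C)/C, which is 34.7, 18.7 and 11.3 for n = 4, 7 and 10.

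**Step 3: dependence on testing frequency.** Suppose references, where they exist, confirm 80% of alerts (illustrative), with r = 1 and only the 7 FST hours fully covered. Coverage at ±30 min is (7 + 163 × 4/24)/170 = 0.201 at 4 tests a day and (7 + 163 × 8/24)/170 = 0.361 at 8. The false alert rate as written is 1 − 0.8 × 0.201 = 83.9% and 1 − 0.8 × 0.361 = 71.1%. Among alerts that have a reference it is 20% in both cases.

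**Step 4: overlap.** Outside the FST, non-overlapping tests at 4 a day leave 1 − 4/24 = 83.3% of the time uncovered at ±30 min. A simulation with random test times between 07:00 and 23:00 gave 84.9%, so the no-overlap assumption slightly understates the effect.

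**Step 5: FST only.** With draws 23 min apart, no point between two draws is more than 11.5 min from one, so nothing is uncovered at either window. One lost draw at that spacing leaves a 46-min gap: fully covered at ±30 min, but (46 − 30)/46 = 35% of it uncovered at ±15 min.

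**The case against.** The strongest reply is that the harm depends on a condition nobody has shown. Protocol 14.8.2 has a fingerstick pairing rule and SAP 6.6.2 drops it, item (3) ties the setting to YSI alone, and the Protocol version history records, for version C, "deleted Home-Use Portion Data Analysis section to remove reference to describing home-use data" (context only). SAP 6.6.4 concerns retention of sensor data and does not say which alerts are scored. The table shells cited in SAP section 9 may show scope and denominator, and they are not in the text available here. The magnitudes run from 11% to 88% and turn on an alert density that the documents do not give. The analysis is retrospective and descriptive.

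Most of this stands as a limit on size. The scope is open and the percentages are illustrative. Alert density is uncertain: readings were visible in the app, subjects were told to confirm by fingerstick before therapy decisions, and tests were advised around meals, all of which favour r above 1; but alerts were switched off (Protocol 7.1.1), so no alert could prompt a test.

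Two things do not fall away. The definitions are complements whatever the scope. And the all-wear reading remains live: in-clinic meter readings taken when YSI is unavailable, or as alternate point-of-care values, are kept out of the analysis (Protocol 9.9.2 and 9.10), so the meter values named in all four definitions would come mainly from outside the FST. A rule that defines a rate belongs in the SAP body even if the shells imply it.

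**Conclusion.** The concern holds. As written, the rule scores an alert with no reference in its window as false. If alerts outside the FST are scored, the true and false alert rates mix sensor error with testing frequency: a sensor whose alerts are all correct would show between 11% and 79% false at ±30 min across the scenarios above, and more at ±15 min. If only FST alerts are scored against YSI, the artefact is near zero, apart from session ends, missed draws and YSI values deleted under the 5% rule (SAP 6.6.3).

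The effect is confined to the two descriptive alert rates. Detection and missed-detection rates start from reference events and do not share the defect; the four primary criteria and study success are untouched. The strict versus inclusive boundary mismatch is real but small. The plan should be changed, though nothing in the primary conclusion depends on it.

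**What to change.** In SAP 7.12:

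1. State which alerts are scored: FST only, or all wear.
2. Limit the denominator of the true and false alert rates to alerts with at least one reference value in the ±30 (or ±15) min window.
3. Report the remaining alerts as not evaluable, with counts.
4. Give YSI-based FST rates and meter-based rates separately, with the YSI-based rate as the main one.
5. Use inclusive boundaries (at or below, at or above) in all four definitions.

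The cost is a few sentences and one filter in the program, with no new data. Fewer alerts will enter the rates. The meter-based rate will be conditional on when subjects chose to test, which can select alerts; that is the reason for leading with the YSI-based rate. That ordering is a reporting choice; items 1 to 3 are the core correction.

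### SAP 7.12 uses an inclusive event definition for the detection rates and a strict one for the true- and false-alert rates, so an alert whose window only ties with the setting counts as a detected event in one table and a false alert in another

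*SAP*

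**What the plan says.** All the relevant text is in SAP 7.12, Simulation Alert Calculation.

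- **Alert settings, item (3).** They are inclusive on both sides: "For hypo range, the CGM alert settings will be set as <= 50/60/70/80/90/100 mg/dL, respectively" and "For hyper range, the CGM alert settings will be set as >=300/250/220/180 mg/dL, respectively". The same item makes the reference threshold move with the alert setting.
- **Detection and missed-detection rates, items (4) 1) and 2).** The qualifying reference is one that "goes at/below (for hypo) or at/above (for hyper) the specified CGM setting levels". A tie counts.
- **False and true alert rates, items (4) 3) and 4).** The qualifying reference is one that "goes below (for hypo) or above (for hyper) the specified CGM setting levels". A tie does not count. A false alert needs no such reference anywhere in the window; a true alert needs at least one.
- **Window.** For items 3) and 4) the search is "within 30 minutes (or 15 minutes) before or after the sensor alarmed at the specified alert settings". Items 1) and 2) use the same lengths, centred on the reference.
- **Label of item 4).** "True Alert (% of Alerts Verified by Hypo/Hyper Events". The only hypo and hyper events that the section defines are the inclusive ones in items 1) and 2).

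Neither document explains the difference or gives a rule for ties. Protocol 5.2.2 lists alert performance as a descriptive endpoint and does not define these rates.

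**The concern.** The four rates are meant to describe one set of alerts against one set of reference events, and a reader comparing the tables will assume a single event definition. Coded literally, the SAP uses two. Every reference strictly beyond the setting is also at or beyond it, but not the reverse, so the mismatch works in one direction only: some alerts that match an event under items 1) and 2) are listed as false under item 3). A larger sample does not remove this.

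The wording applies to the threshold, predictive and combined alert types, to all ten settings (six hypo, four hyper) and to both window lengths. Validation under SAP section 8 may not catch it. Two programmers who code the text literally will agree with each other, and two who resolve the tie differently will disagree with nothing in the SAP to settle it.

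**Working it through.** The documents state no alert rate, so there is no figure of the plan's to reproduce. The check has two parts.

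**1. Logic.** Write s for the setting and r for any reference in the window.

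- Hypo event (items 1, 2): some r ≤ s. Hypo true alert (item 4): some r < s. False alert (item 3): no r < s.
- Hyper: the same with ≥ and >.

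The windows are symmetric and equally long, so an alert and a reference that match under one definition also match under the other. Applied to example windows in which an alert has fired:

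| Setting | References in window (mg/dL) | Event detected | Alert as written | Alert with inclusive rule |
|---|---|---|---|---|
| Hypo 70 | 78, 70, 75 | yes | false | true |
| Hypo 70 | 78, 70, 69 | yes | true | true |
| Hypo 70 | 78, 71 | no | false | false |
| Hyper 180 | 170, 180, 176 | yes | false | true |
| Hyper 180 | 170, 180, 181 | yes | true | true |

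Only windows whose most extreme reference equals the setting change. One reference beyond the setting makes the alert true under either wording.

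**2. Illustrative size.** All inputs here are assumptions. Given an alert at setting 70, the underlying reference level is Normal with mean 70 and SD 10 or 20; references scatter around it with SD 4; the window holds 1, 3 or 5 references; values are rounded to the recording step. The quantity is the share of alerts whose lowest reference equals 70 exactly, that is, the alerts that move from false to true under the inclusive rule.

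| Recording step | SD 10 (1 / 3 / 5 references) | SD 20 (1 / 3 / 5 references) |
|---|---|---|
| 0.1 mg/dL | 0.4 / 0.4 / 0.4% | 0.2 / 0.2 / 0.2% |
| 0.5 mg/dL | 1.9 / 1.8 / 1.8% | 0.9 / 1.0 / 1.0% |
| 1 mg/dL | 3.7 / 3.6 / 3.4% | 2.0 / 2.0 / 1.9% |

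Hand check for one reference: the tie probability is about step × 0.399 / √(SD² + 4²). With SD 10 and step 1 this is 0.399 / √116 = 0.399 / 10.77 = 0.037. With SD 20 and step 0.1 it is 0.1 × 0.399 / √416 = 0.0399 / 20.40 = 0.002. Both agree with the table.

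As rates, for step 1, SD 10 and three references, the true-alert rate goes from 60.9% as written to 64.5% with the inclusive rule. The false-alert rate goes from 39.1% to 35.5%.

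A separate simulation of hypo threshold alerts (1,500 sessions per setting, draws every 5 or 15 minutes, assumed sensor error SD 12 mg/dL) gave 2.8 to 3.7 points at a 1 mg/dL step for settings 60 to 90, and 1.3 to 1.9 points at 0.5 mg/dL for settings 60 to 80. Hyper, predictive and combined alerts were not simulated.

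On which step is realistic: SAP 6.6.3 uses the mean of the two YSI results in the paired analysis. If each result were a whole number of mg/dL, that mean would fall on a 0.5 mg/dL grid. The SAP does not say whether the mean also feeds the alert analysis, and it describes no averaging for meter values, which are also allowed as references.

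**The case against.** The strongest reply is that the SAP already implies the inclusive rule. Item (3) writes the settings with ≤ and ≥ and ties the reference threshold to them, and item 4) speaks of verification by events that are defined inclusively. On this view the wording of items 3) and 4) is loose English rather than a chosen strict rule. That may well be the intent. It does not remove the conflict: the inclusive phrase appears in both detection items and the strict phrase in both alert items, and a programmer following the text would code two different operators. The mock tables that SAP section 9 refers to were not available and might show the intended rule.

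A second reply is that the choice of inequality is a convention, and strict wording in all four items would also be uniform. That is correct; overstatement here is measured against the SAP's own event definition, not against an outside standard. Inclusive wording is preferable because it matches the alert triggers in item (3).

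Three stronger readings are tempting and do not hold.

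- *Every alert at the setting is scored false, so even an error-free sensor must accumulate false alerts.* The whole window must hold no reference beyond the setting. Protocol 9.9.1 calls for draws about every 5 minutes once the previous value is under 75 mg/dL, so a low-glucose window can hold many references, and one beyond the setting is enough.
- *The study result is affected.* Success rests on criteria 1a) to 1d) only (SAP 7.6), and the documents set no threshold for any alert rate.
- *The rule flatters the device.* It can only make the alert rates look slightly worse.

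**Conclusion.** The inconsistency is in the current SAP text and is worth correcting as a minor point. An alert whose ±15 or ±30 minute window ties with the setting, with no reference beyond it, is counted as a detected event and as a false alert. The direction is certain; the size is not. Under the assumed models it is roughly 0.2 to 3.7 percentage points for recording steps of 0.1 to 1 mg/dL, with the lower part more plausible for YSI if the two-result mean is used for alerts. The upper end needs whole-number references. Recording resolution, sensor error and glucose trajectories are all assumptions, so the range is an illustration and not a bound. The sample size and the pass/fail decision do not change.

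**What to change.** In SAP 7.12, item (4), definitions 3) and 4), replace "goes below (for hypo) or above (for hyper) the specified CGM setting levels" with "goes at/below (for hypo) or at/above (for hyper) the specified CGM setting levels". All four rates then share one event definition that agrees with the inclusive settings in item (3). If the strict rule was intended, the SAP should say so, give the reason, and state how ties are handled in each table.

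The cost is one wording change in two definitions and one comparison operator in the program, plus a rerun of the alert tables if they already exist. The protocol needs no change, because it does not define these rates.
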